If independence from active vitamin D and reduction of oral calcium is not achieved on Day 14 (ie, elimination of active vitamine D and reduction of oral calcium to or below 500 mg/day), the AZP-3601 dose will be increased and patients will be treated at this dose for the remaining duration of the treatment period (up to Day 28). In addition, staggered reductions of doses of oral calcium and active vitamin D supplements will therefore be performed and/or continued during the second 14 days of the Main Treatment Period according to the same principles as the first 14 days of the Main Treatment Period.

Patients achieving independence from active vitamin D and reduction of oral calcium on Day 14 will remain at the same dose level. The last remaining daily dose of oral calcium, if any, may be removed on Day 17 based on the predose albumin-corrected value of serum calcium.

Patients will undergo frequent testing for albumin-corrected serum calcium and phosphate during the initial 14-day treatment period and again following increase of the dose. In addition, there may be additional and unscheduled checks for albumin-corrected serum calcium and phosphate at the discretion of the Investigator.

At any time during the study, hypercalcemia and hypocalcemia will be managed by adjustment in active vitamin D and/or oral calcium supplementation. Adjustments will be based on laboratory values including albumin-corrected serum calcium and serum phosphate as well as on symptoms and will be performed at the Investigator's judgment. As a general guidance, adjustments should be performed when calcium values are outside the target range of 7.8 to 9.0 mg/dL, ie, 1.95 to 2.25 mmol/L.

The following treatments are administered in Part C in an open-label fashion:

- Cohort C1: multiple sc doses of 20 µg AZP-3601 (n=12) qd from Day 1 to Day 28 (dose increase of AZP-3601 to 40 µg was allowed from Day 14 onwards)
- Cohort C2^b: multiple sc doses of a fixed dose of 10^a µg AZP-3601 (n=12) qd from Day 1 to Day 28 (dose of AZP-3601 may be increased at a fixed dose of 20^a µg from Day 14 onwards)

During the extension phase, patients may have their AZP-3601 dose increased in increments of 10^a µg to a maximum dose of 60^a µg (Cohort 1) and of 80^a µg (Cohort 2)

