	for supplemental oral calcium treatment ≥1000 mg per day over and above
	normal dietary calcium intake prior to baseline measurements.
	- Part C (Extension phase): Patients entering the extension phase need to
	have completed the Day 28 visit of the Main treatment period and sign the
	ICF before entering the extension phase.
Sex	: Male or female
Age	: 18 to 75 years, inclusive, at screening

Study Drug

Active medication	
Drug product	: AZP-3601
Activity	: PTH analog
In development for	: HP
Strength	:40 μg of AZP-3601 per vial
Dosage form	: Powder for solution for injection
Route of administration	: sc abdominal injection (with rotation of injection sites every dosing day for Parts B and C)
Manufacturer	: NUVISAN GmbH, Neu-Ulm, Germany

Active medication (additional batch for Part C)

Drug product	: AZP-3601
Activity	:PTH analog
In development for	: HP
Strength	:100 μg of AZP-3601 per vial *
Dosage form	: Powder for solution for injection
Route of administration	: sc abdominal injection (with rotation of injection sites every dosing day)
Manufacturer	: NUVISAN GmbH, Neu-Ulm, Germany

Variables* Safety and Tolerability Variables

: Adverse events, clinical laboratory (clinical chemistry, hematology, coagulation, and urinalysis), vital signs (systolic and diastolic blood pressure, pulse rate, and body temperature), 12-lead electrocardiogram and time-matched with PK sampling (Part C), continuous cardiac monitoring (, body weight, physical examination (full or abbreviated), injection site reaction, and presence of antidrug antibodies (ADA) in plasma (ADA for Part C only)

F	or hypocalcemia and hypercalcemia events, time of onset, amount of upplements administered, and timing will be recorded.
PK Variables : -	Plasma AZP-3601 concentrations Plasma PK parameters estimated using noncompartmental analysis, as appropriate.
	Day 1 of Part C: Cmax, tmax, AUC0-t, AUC0-12, and AUC0-24. Day 28 of Part C (Main treatment period) and Day 84 of Part C (Extension phase): Cmax, Ctrough, Cmin, tmax, kel, t1/2, AUC0-12, AUC0-24, CLss/F, Vz/F, and Rac
PD and Other	
Variables : P -	arts C : Levels of serum total calcium, albumin-corrected serum calcium, and serum
-	phosphate. 24-hour urine calcium, phosphate, renal clearance of calcium and phosphate, fractional excretion (FECa) of calcium and phosphate,
	renal tubular maximum reabsorption of phosphate/glomerular filtration rate (TMP/GFR).
-	Endogenous serum PTH(1-84) levels.
: P	arts C only:

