- b These visits are mandatory. As an alternative, these visits may be performed off-site; for instance, blood sampling may be performed at a local laboratory or at home by a study nurse. In addition, during the optimization period, there may be optional weekly visits.
- c A full physical examination will be done at screening, and on Day 28 (predose). An abbreviated physical examination will be done on Days 1, 14, and 16 (at predose), and 29, and at follow-up. Unscheduled symptom-directed physical examinations may be conducted at any time per the Investigator's discretion.
- d Single 12-lead ECG: at screening. The ECG will be recorded after the subject has been resting for at least 5 minutes in the supine position.
- e Supine systolic and diastolic blood pressure, pulse rate, and body temperature: at screening, on Day -1, on Days 1, 14, 15, and 28 at predose, on Day 29, and at follow-up. Vital signs will be recorded after the subject has been resting for at least 5 minutes in the supine position.
- f Subjects in Part C will receive AZP-3601 for 28 days as daily sc abdominal injections (with rotation of injection sites every dosing day). During the study visit the injection will be performed at the clinical site.
- g Blood sampling for ADA: on Day -1, on Day 28, and at follow-up. All samples will be analyzed. In case of positive ADA, patients will be monitored until the levels return to normal.
- h Injection site reaction: postdose on Day 1, predose and 1 hour postdose (when dosing) on Days 14, 15, 16, and 28, on Day 29, and at follow-up.
- i Blood sampling for PK of AZP-3601 in plasma: serial samplings on Days 1, 14, and 28 (predose, 5min, 10min, 20min, 30min, 1 hour and 2 hours post dose).
- j Serial sampling on Days 1, 14, and 28 (predose, 2 hours and 6 hours post dose). Samples will be taken fasting and pre-dose, except when profile where pre- and post-doses are taken
- k At any time during the study, hypercalcemia and hypocalcemia will be managed by adjustment in active vitamin D and/or oral calcium supplementation. Adjustments will be based on laboratory values including albumin-corrected serum calcium and serum phosphate as well as on symptoms and will be performed at the Investigator's judgment.
- Bone turnover biomarkers include serum bone-specific alkaline phosphatase, serum carboxy-terminal telopeptide of type I collagen, serum procollagen type 1 amino-terminal propeptide, and serum osteocalcin.

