15.1.1.2 Plasma PK Parameters

PK Parameters for AZP-3601 as defined in Table 1

EDSREP 009 T 01 G Page 20 of 53

Statistical Analysis Plan AZP20005-20005X

Protocol: AZP-3601-CLI-001 Version Date: 26-Aug-2022

Table 1 Plasma AZP-3601 PK Parameters

Parameter	AND C Day 1	AND PART C DAY 28 and DAY 84	Description	SAS Programming Notes
C _{max}	×	Х	Maximum plasma concentration. Observed peak analyte concentration obtained directly from the experimental data without interpolation, expressed in concentration units.	Cmax from WNL. C_{max} will be presented as "Cmax" in the TFL.
Ctrough		Х	Trough plasma concentration.	Derived in SAS C_{trough} will be presented as "Ctrough" in the TFL.
C _{min}		Х	Minimum plasma concentration (predose concentration excluded)	Cmin from WNL. C _{min} will be presented as "Cmin" in the TFL.
t _{max}	×	Х	Time to maximum plasma concentration. First observed time to reach peak analyte concentration obtained directly from the experimental data without interpolation, expressed in time units.	Tmax from WNL. t _{max} will be presented as "Tmax" in the TFL.
AUC _{0-t}	×		Area under the plasma concentration-time curve (time 0 to time of last quantifiable concentration).	AUClast from WNL. AUC _{0-t} will be presented as "AUClast" in the TFL.
AUC _{0-inf}	X		Area under the plasma concentration-time curve (time 0 to infinity). Calculated as: $AUC_{0-inf} = AUC_{0-t} + C_{last}/k_{el}$, where C_{last} is the observed concentration at time t, where t is the last point with a concentration above the lower limit of quantification. Percent extrapolation less than or equal to 20% and an adjusted r^2 greater than 0.80 are required to obtain a reliable AUC_{0-inf} .	AUCINF_obs from WNL. AUC _{0-inf} will be presented as "AUCinf" in the TFL. If %AUC _{extra} >20% then parameter is flagged. If Adj $R^2 \le 0.80$ then parameter is

EDSREP 009 T 01 G Page 21 of 53

Version Date: 26-Aug-2022

Parameter	AI C Da		8	SAS Programming Notes
				flagged.
%AUC _{extra}			Percentage of estimated part for the calculation of AUCinf: Calculated as: ([AUC _{0-inf} – AUC _{0-t}]/ AUC _{0-inf})*100%.	AUC_%Extrap_obs from WNL. %AUC _{extra} will be presented as "AUC%extrap" in the TFL, and listed only.
AUC ₀₋₆		Х	Area under the plasma concentration-time curve from time zero up to 6 hours.	AUC0-6 from WNL AUC0-6 will be presented as "AUC(0-6)" in the TFL.

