AUC ₀₋₁₂		Х	Area under the plasma concentration-time curve from time zero up to 12 hours.	AUC0-12 from WNL AUC0-12 will be presented as "AUC(0-12)" in the TFL.
AUC ₀₋₂₄		Х	Area under the plasma concentration-time curve from time zero up to 24 hours.	AUC0-24 from WNL AUC0-24 will be presented as "AUC(0-24)" in the TFL.
k _{el}		X	Terminal phase rate constant calculated by linear regression of the terminal log-linear portion of the concentration vs. time curve. Linear regression of at least three points and an adjusted r² greater than 0.80 are required to obtain a reliable kel.	Lambda_z from WNL. k_{el} will be presented as "Kel" in the TFL, and listed only If Adj $R^2 \le 0.80$ then parameter is flagged.
t _{1/2}		X	Terminal phase half-life expressed in time units. adjusted $\rm r^2$ greater than 0.80 is required to obtain a reliable $\rm t_{1/2}$.	HL_Lambda_z from WNL. $t_{1/2}$ will be presented as "t1/2" in the TFL. If Adj $R^2 \le 0.80$ then parameter is flagged.

EDSREP 009 T 01 G Page 22 of 53

Statistical Analysis Plan AZP20005-20005X Protocol: AZP-3601-CLI-001 Version Date: 26-Aug-2022

				VOIDION Bato. 20 7 tag 2022
Parameter	AND C Day 1	AND PART C DAY 28 and DAY 84	Description	SAS Programming Notes
CL/F			Apparent oral clearance, calculated as dose/AUC _{0-inf} .	CL_F_obs from WNL. If %AUC _{extra} >20% or Adj R ² ≤ 0.80 then parameter is flagged.
CL _{ss} /F		X	Apparent oral clearance at steady state, calculated as dose/AUC _{0-tau} where tau =6h (Parts B and C).	CLss_F from WNL CLss/F will be presented as "CLss/F" in the TFL.
Vz/F		Х	Apparent volume of distribution at terminal phase, calculated as (CL/F)/kel (Part A), or as (CLss/F)/kel (Parts B and C).	VZ_F_obs from WNL. If %AUC _{extra} >20% or Adj R ² ≤ 0.80 then parameter is flagged.
Rac		Х	Accumulation ratio, based on AUC _{0-tau} of Day 14 (Part B) or Day 28 (Part C) vs Day 1 where tau = 6h (Parts B and C).	Calculated in SAS. Rac will be presented as "Rac" in the TFL.
Adj R²	X		Goodness of fit statistic for the log-linear terminal elimination phase of the concentration-time profile identified by least-squares linear regression and adjusted for the number of points (minimum of 3) used in the estimation of k_{el} .	"Rsq_adjusted" from WNL. Adj R ² will be presented as "Adj R2" in the TFL and listed only.

Note: AUCs will be calculated using linear up / log down, expressed in units of concentration x time.

EDSREP 009 T 01 G Page 23 of 53

Version Date: 26-Aug-2022

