15.2 Pharmacokinetic Summaries

15.2.1 Pharmacokinetic Concentrations

All AZP-3601 plasma concentrations will be reported under PK population set with data handling of PK Data Set and PK Data Set Info (for information only). Under PK Data Set, analyses on the concentrations will be performed with values under LLOQ set as "BQL". Under PK Data Set Info, AZP-3601 plasma concentration will include the concentrations extrapolated from the analyte response under the LLOQ (for information purpose); values under LLOQ will either be a "No peak" or an actual value between 0 and the LLOQ value (i.e. 50 pg/mL). The Inclusion of the informative PK concentrations ("No peak" and actual value between 0 and the LLOQ) in the analyses under PK Data Set Info will be performed for information only. The conventions to be applied for "No peak" under PK Data Set Info will be the same as the one use for BQL under PK Data Set. Descriptive statistics and PK concentration plots will be conducted on both data sets.

Descriptive statistics (n, 0<n<LLOQ, n with imputed 0, arithmetic mean, SD, geometric mean, geometric CV(%), median, min, and max) will be used to summarize the plasma concentrations for AZP-3601 by scheduled time point by study part and treatment (for Parts A and B)/cohort (for Part C). Plasma concentrations for AZP-3601 below the quantifiable limit (BQL) will be set to zero in the computation of descriptive statistics. Geometric means and geometric CV(%) will be presented as 'NC' (not calculable) if there is at least one BQL value imputed by zero.

Linear and semi-logarithmic plots of the arithmetic mean plasma concentration with SD by scheduled
sampling time will be provided by study part and
plots will show time in hours. In Part
C, the MAD treatments will be presented in one plot per day. In addition, overlay plots for the MAD
treatments will be presented,
showing Day 1, Day 14 and Day 28 in one plot for Part C (one plot per cohort). If more than half of the subjects for a given timepoint have BQL values, then no mean profiles will be provided.
Combined individual concentration-time profiles will be presented graphically on both a linear and a semi-logarithmic scale for each

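### Part C Day 14 PK is reported only as concentrations, while Day 28 parameters and the accumulation ratio are pooled by cohort across response-dependent doses

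*SAP*

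**What the plan says.** Protocol Table 3, footnote i, schedules one sampling scheme for three days: "serial samplings on Days 1, 14, and 28 (predose, 5min, 10min, 20min, 30min, 1 hour and 2 hours post dose".

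Parameters are planned for fewer days. Besides Day 1, the protocol synopsis (PK Variables) names "Day 28 of Part C (Main treatment period) and Day 84 of Part C (Extension phase", and the matching column of SAP Table 1 is headed "AND PART C DAY 28 and DAY 84". Rac is an AUC ratio "of Day 14 (Part B) or Day 28 (Part C) vs Day 1 where tau = 6h (Parts B and C".

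SAP 15.2.1 does use the Day 14 samples as concentrations. They are summarised "by scheduled time point by study part and treatment (for Parts A and B)/cohort (for Part C", and overlay plots are planned "showing Day 1, Day 14 and Day 28 in one plot for Part C (one plot per cohort". SAP 15.2.2 summarises the derived parameters by cohort in Part C.

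On dosing, the protocol synopsis says: "Patients achieving independence from active vitamin D and reduction of oral calcium on Day 14 will remain at the same dose level". Patients who miss that criterion have the dose increased for the rest of the 28 days.

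**The concern.** PK after single and multiple doses in patients is a named secondary objective (protocol synopsis; SAP 5.2). Three multiple-dose profiles are drawn in Part C, and only Day 14 comes before dosing starts to follow response. By Day 28 a cohort may be on two dose levels, split by whether supplements could be withdrawn. By Day 84 doses have been titrated individually, up to 60 or 80 µg.

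Parameters are derived on the two mixed-dose days and not on the common-dose day. The Day 28 cohort summaries of Cmax, Ctrough and AUC then describe no single dose. A Rac above 1 could come from accumulation, from escalation or from both, and the cohort table cannot tell these apart.

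**Working it through.** **Step 1. Set the Part C profile days side by side** (protocol Tables 3 and 4 and PK Variables; SAP Table 1).

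| Day | Points | Dose state | Parameters defined |
|---|---|---|---|
| 1 | 7 | First dose, single | Cmax, tmax, AUCs |
| 14 | 7 | About two weeks on the first dose (see step 5) | None |
| 28 | 7 | First or increased dose, set by Day 14 response | Cmax, Ctrough, Cmin, tmax, AUCs, kel, half-life, CLss/F, Vz/F, Rac |
| 84 | 7 | Individually titrated | As Day 28, though the Rac definition names Day 28 |

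The Day 14 plan comes to at most 7 × 24 = 168 samples, from two cohorts of about 12.

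**Step 2. Could redaction hide a Day 14 entry?** Part of the SAP Table 1 column header is missing, but two readable places settle it. The Rac row assigns Day 14 to Part B and Day 28 to Part C, and the protocol list gives only Days 1, 28 and 84 for Part C. SAP 7.1 (Changes from Protocol) does not mention Day 14.

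**Step 3. Does the grouping separate the doses?** SAP 15.2.2 groups by cohort. In SAP 8.2.2 the dose-level label for each cohort already contains the permitted increase, so it does not separate them either. No dose normalisation is stated for Rac.

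**Step 4. How far could escalation move Rac?** The documents give no Rac, escalation rate or PK variability, so there is no stated figure to reproduce. What follows is an illustration.

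- From the protocol: C1 goes from 20 to 40 µg and C2 from 10 to 20 µg, so the dose ratio is r = 40/20 = 20/10 = 2.
- Assumed: AUC proportional to dose, true accumulation ratio 1, and a fraction f of the cohort escalated and at the higher dose on Day 28.
- Each patient's Rac is then 1 if not escalated and r if escalated.
- Geometric mean Rac = 1^(1−f) × r^f = r^f. Arithmetic mean = (1−f) + f × r.

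| f | Geometric mean, r = 2 | Arithmetic mean, r = 2 |
|---|---|---|
| 0 | 1.00 | 1.00 |
| 0.25 | 2^0.25 = 1.19 | 0.75 + 0.50 = 1.25 |
| 0.50 | 2^0.50 = 1.41 | 0.50 + 1.00 = 1.50 |
| 0.75 | 2^0.75 = 1.68 | 0.25 + 1.50 = 1.75 |
| 1 | 2.00 | 2.00 |

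SAP 6.0 and 8.2.2 still show 40 and then 60 µg for C2. With r = 60/40 = 1.5, the geometric means are 1.5^0.25 = 1.11, 1.5^0.50 = 1.22 and 1.5^0.75 = 1.36. The protocol and SAP doses for C2 differ and need reconciling, but the direction is the same with either.

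Under the same assumptions a Day 14/Day 1 ratio at a common dose is 1.00 for every f.

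**Step 5. Is Day 14 at the first dose?** The protocol treatment list and SAP 6.0 and 8.2.2 allow an increase starting on Day 14. SAP 14.0 counts increases at Day 15, and after Day 15, against Day 1, which implies that the Day 14 injection is still the first dose. The predose sample on Day 14 follows the Day 13 injection, so it is at the first dose on either reading. The six postdose samples depend on which text applies.

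**The case against.** A reader might infer that multiple-dose exposure at the first dose is left to a small, response-selected group on Day 28. The documents do not support this. SAP 15.2.2 pools everyone in the cohort, and no Day 28 first-dose subset appears in the readable text. Nor is any confidence interval for a PK geometric mean planned that a smaller subset would widen. It would also be wrong to say that the Day 14 samples go unused: SAP 15.2.1 gives tables by time point and plots, with individual listings, and the Day 14 predose row is in effect the trough.

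Other points for the plan as written are fair:

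- Protocol and SAP agree on Days 1, 28 and 84, so there is no contradiction. End-of-period profiles are a legitimate choice in an exploratory, descriptive study.
- Day 1 already gives first-dose Cmax, tmax and AUC in unselected patients. SAP 7.1 expects rapid elimination, so Days 1 and 14 may differ little.
- CLss/F divides dose by AUC and is therefore dose-adjusted by construction. The mixing affects Cmax, Cmin, Ctrough, AUC and Rac.
- The text of SAP 15.2.2.1 (Dose-Proportionality) and the table shells are not available, so handling by dose there cannot be excluded.

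These points lower the priority but do not remove the issue. Concentration tables do not replace individual parameters: peak, time of peak and AUC per patient cannot be recovered from means at scheduled times. Under SAP 15.2.1 a single value below quantification makes the geometric mean and CV at that time point not calculable. If accumulation is expected to be negligible, a same-dose ratio is the direct way to show it, and the pooled Day 28 ratio could suggest the opposite.

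**Conclusion.** The point holds in limited form. Neither document defines a Part C Day 14 parameter, although a full profile is scheduled. The planned Day 28 exposure summaries and Rac combine dose levels assigned by Day 14 response, with no dose adjustment stated in the readable text.

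The apparent Rac of 1.19 to 1.68 shows how large the effect could be and does not predict what will be seen. It rests on assumed dose proportionality, no true accumulation and escalation of 25% to 75%. If nobody escalates, the problem disappears. The gain from Day 14 also depends on that day's injection being at the first dose, which SAP 14.0 supports but other text leaves open. The documents give no evidence that exposure differs between patients who do and do not escalate, so no selection bias in PK is claimed.

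This is a nearly free improvement of low to moderate priority.

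**What to change.** 1. Add Part C Day 14 to SAP Table 1 and section 15.2.2 for Cmax, tmax, Ctrough and AUC to the last quantifiable sample. Sampling stops at 2 h, so this AUC is better supported than one to 6 h.
2. Label each Day 14 profile by the dose actually injected that day.
3. Present Day 14 beside Day 1 with a within-patient Day 14/Day 1 ratio, restricted to patients on the same dose both days. For AUC, use the same time interval on both days. Make this the main same-dose multiple-dose result.
4. Footnote the Day 28 parameters and Rac as pooled across dose levels, with the number of patients at each dose.
5. Reconcile the text allowing an increase from Day 14 with the Day 15 definitions in SAP 14.0.

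The cost is one more non-compartmental run on samples already scheduled and one more block in the parameter table. No sampling, visit or treatment rule changes.

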- The schedule of assessment indicates the end of collection day of each 24h collection. Refer to Section 3.5.1.3.2 and Figure 4 for more details.
- m Testing may be performed at the discretion of the Investigator. Testing will be performed using a country registered detection test
- n Samples will be taken predose and fasting
- o Dispense the study drug to the patients on Day 28. Study drug return/dispense on Day 56 and Study drug return on Day 84
- p On Day 29 and Day 30, the subjects will follow the same assessments than ones listed in Table 3, except:
 - Blood Sampling: Total Calcium/Albumin- Corrected Calcium/Phosphate and Creatinine in Serum, taken predose in addition to fasting
 - Physical Exam and Vital signs at predose
 - Injection site reaction at pre-dose and at 1-hour postdose.
- q DXA scans can be obtained within 2 weeks prior to the end of the extension phase visit (Day 84 visit).
- r Blood sampling for PK of AZP-3601 in plasma: serial samplings on Day 84 (predose, 5min, 10min, 20min, 30min, 1 hour and 2 hours post dose).

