7.1 Changes from Protocol

The PK parameter AUC₀₋₆ will be provided whereas AUC₀₋₁₂ and AUC₀₋₂₄ will not be provided, because the drug is expected to eliminate quickly and because of the scheduled timepoints of PK assessments.

The PK parameter AUC_{0-inf} will be calculated at Day 1 for Control C, therefore kel will be also calculated at this timepoint as well as Adj R².

An additional analysis set (Enrolled Set) will be derived for Part C. The adverse events (AEs) in Part C will also be summarized for Enrolled Set.

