15.2.2 Pharmacokinetic Parameters

PK parameters for AZP-3601 will be estimated using non-compartmental methods with WNL under PK population set with data handling of PK Data Set and PK Data Set Info (if meaningful by the data obtained). Parameters will first be derived with values under LLOQ set as "BQL" (i.e. using PK Data Set). The inclusion of the informative PK concentrations ("No peak" and actual value between 0 and the LLOQ) in the calculation of the parameters will be performed for information only (i.e. using PK Data Set Info). Descriptive statistics will be conducted on both data sets if meaningful by the data obtained.

The plasma PK parameters will be estimated from the concentration-time profiles. In estimating the PK parameters, BQL values at the beginning of the profile will be set to zero. BQL values that occur after the first quantifiable point will be considered missing. Values that are embedded between BQLs, or quantifiable values occurring after two or more BQLs, will be set to missing at the discretion of the pharmacokineticist. Actual sampling times, rather than scheduled sampling times, will be used in all computations involving sampling times. If the actual time or dose time is missing, the scheduled time may be substituted in order to calculate the PK parameter.

EDSREP 009 T 01 G Page 24 of 53

Version Date: 26-Aug-2022

The points to be included in the k_{el} range will be determined by the pharmacokineticist after inspection of the semi-log concentration-time profiles. At least 3 points will be required to be used. The C_{max} data point will not be included.

Parameters based on %AUC $_{extra}$ >20% or Adj R 2 \leq 0.80 will be flagged but not excluded from statistical analysis.

Descriptive statistics (n, arithmetic mean, SD, geometric mean, geometric CV(%), median, min, and max) will be used to summarize the calculated PK parameters by study part and treatment (for Parts A and B) /cohort (for Part C). For t_{max}, only n, median, min and max will be presented.

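### Part C PK sampling stops 2 hours after the dose, but the SAP's steady-state AUC, CLss/F and Rac use a 6-hour window, so they depend on extrapolation or cannot be calculated

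*SAP*

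**What the plan says.** **Sampling.** Protocol Table 3, footnote i, sets the Part C main-period PK draws: "serial samplings on Days 1, 14, and 28 (predose, 5min, 10min, 20min, 30min, 1 hour and 2 hours post dose". Table 4, footnote r, repeats the same times for the extension: "serial samplings on Day 84 (predose, 5min, 10min, 20min, 30min, 1 hour and 2 hours post dose". No Part C PK draw is scheduled after 2 hours. Blood is drawn at 6 hours on the same days, but for calcium and phosphate: "Serial sampling on Days 1, 14, and 28 (predose, 2 hours and 6 hours post dose" (Table 3, footnote j; Table 4, footnote i, does the same for Days 56 and 84).

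**Parameters.** SAP 7.1 replaces AUC0-12 and AUC0-24 with AUC0-6, "because the drug is expected to eliminate quickly and because of the scheduled timepoints of PK assessments". SAP Table 1 defines AUC0-6 as the "Area under the plasma concentration-time curve from time zero up to 6 hours". It computes CLss/F as dose over AUC0-tau, "where tau =6h (Parts B and C", and uses the same tau for Rac (Day 28 against Day 1). Vz/F is CLss/F divided by kel. Table 1 still lists AUC0-12 and AUC0-24.

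**Calculation rules (SAP 15.2.2).** For kel, "At least 3 points will be required to be used", and the Cmax point is left out. Also, "BQL values that occur after the first quantifiable point will be considered missing". Parameters with more than 20% extrapolated AUC or a poor terminal fit are flagged and stay in the summaries.

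**The concern.** The window over which exposure is computed runs 4 hours past the last concentration. The SAP names Part C when it sets tau to 6 hours, so this does not read as a rule meant only for Part B. One of the two reasons in SAP 7.1, the PK schedule, does not fit the Part C schedule in the protocol. SAP version 3.0 was revised to bring in the Day 84 PK samples (SAP 4.0) and kept the 6-hour window.

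Nothing says how AUC0-6 is obtained when the last concentration is at or before 2 hours. The natural route is extrapolation with kel; without kel, no route is described. Late values below quantification count as missing, so they cannot close the curve at zero either.

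PK in patients is a secondary objective, and exposure, clearance and accumulation are its main outputs. If AUC0-6 is calculable only in patients with early peaks, the summaries for cohorts of about 12 would cover a subset chosen by the shape of the profile. A largely extrapolated AUC0-6, CLss/F or Rac could also be summarized unmarked, because Table 1 sets no flag on those three.

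**Working it through.** The plan has no figure of its own to reproduce here: there is no hypothesis test and no stated half-life or tmax.

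**Step 1. Compare the windows.** Last PK draw 2 h (Protocol Tables 3 and 4); upper AUC limit 6 h (SAP Table 1). Unsampled: 6 - 2 = 4 h, or 4/6 = 67% of the interval in clock time.

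**Step 2. Count the points left for kel.** Post-dose draws are at 5, 10, 20, 30, 60 and 120 min. Removing the Cmax point and everything before it leaves:

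| tmax | points, all quantifiable | points, 2 h value below quantification |
|---|---|---|
| 5 min | 5 | 4 |
| 10 min | 4 | 3 |
| 20 min | 3 | 2 |
| 30 min | 2 | 1 |
| 1 h | 1 | 0 |
| 2 h | 0 | 0 |

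With a minimum of 3, kel fails when tmax is 30 min or later, and at 20 min if the 2 h value is below the 50 pg/mL limit (SAP 15.2.1). AUC0-6, CLss/F, Vz/F and Rac fail with it.

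**Step 3. Share of AUC0-6 lying after 2 h.** Half-life and tmax are assumptions.

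- Bolus-like decay, k = ln2/t1/2: share = (e^(-2k) - e^(-6k)) / (1 - e^(-6k)). At t1/2 = 1 h this is (0.25 - 0.0156)/(1 - 0.0156) = 23.8%.
- One compartment with first-order absorption: AUC0-T is proportional to (1 - e^(-kT))/k - (1 - e^(-ka T))/ka, with ka solved from tmax = ln(ka/k)/(ka - k). At t1/2 = 1 h and tmax = 20 min, k = 0.693 and ka is about 8.05. AUC0-2 is then 1.082 - 0.124 = 0.958 and AUC0-6 is 1.420 - 0.124 = 1.296, so the share is 1 - 0.958/1.296 = 26.1%.

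| assumed t1/2 | bolus-like | absorption, tmax 20 min |
|---|---|---|
| 0.25 h | 0.4% | 1.8% |
| 0.5 h | 6.2% | 8.3% |
| 1 h | 23.8% | 26.1% |
| 1.5 h | 36% | 37.6% |
| 2 h | 42.9% | 44.5% |

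Moving tmax between 10 and 30 min changes the share little: 6.8-12.1% at 0.5 h, 24.6-28.4% at 1 h and 43.5-45.8% at 2 h. In the bolus-like case the share passes 20% at a half-life of about 0.88 h.

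**Step 4. Look for an AUC within the sampled window.** AUC0-t appears for Day 1 in the protocol's list of PK variables, and the marks in SAP Table 1 agree as far as they can be read. On Days 28 and 84 the listed AUCs are 0-6, 0-12 and 0-24 h, and SAP 7.1 drops the last two. The only steady-state AUC left therefore ends 4 hours after the last sample.

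**The case against.** The strongest reply is that the SAP gives rapid elimination as its first reason for the shorter window. If the half-life is 0.5 h or less, the tail is only about 2-8% of AUC0-6, and extrapolating it with kel does little harm. Four of the six post-dose draws fall within 30 minutes, which suggests that an early peak is expected. This stands as a limit on the size. It does not remove the mismatch, and fast elimination cuts both ways: it also pushes late samples below quantification and removes points that kel needs.

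There are safeguards. The flag in SAP 15.2.2 is worded generally, and Table 1 applies it to Vz/F. Since AUC0-inf is at least AUC0-6, the extrapolated share of AUC0-6 cannot exceed that of AUC0-inf. An informational rerun uses values below the quantification limit where meaningful. Cmax, tmax and Day 1 AUC0-t need no 6-hour window. What remains is that AUC0-6, CLss/F and Rac carry no flag of their own.

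Stronger readings are tempting, and the documents do not support them:

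- **Two thirds of exposure is unobserved.** The 67% is clock time, not area.
- **The parameters will generally be missing.** That needs late peaks or late values below quantification, and no tmax is given.
- **The Cohort C1 to C2 decision rests on these values.** SAP 7.2 lists plasma concentration, not AUC0-6 or Rac, as the PK item of the interim report.

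On sources: the SAP's schedule appendix was not in the text available, some Table 1 column marks are damaged, and the protocol and SAP differ on Cohort C2 doses, so they may reflect different protocol versions. If the appendix shows a later Part C PK draw, the two schedules must be reconciled instead.

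**Conclusion.** The plan is wrong as written on this point. The mismatch is explicit and needs no assumption: Part C concentrations stop at 2 h, while AUC0-6, CLss/F and Rac, and Vz/F through CLss/F, need 6 h. Following the plan gives extrapolated values, or none where fewer than three quantifiable points follow Cmax.

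The numerical effect is open. It could be minor (about 2-8% of AUC0-6 at half-lives of 0.25-0.5 h) or substantial (about 26-45% at 1-2 h), under one compartment with tmax of 20 min. These shares measure reliance on extrapolation, not bias. The number of patients affected cannot be derived from the documents.

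Severity: should be fixed. The parameters are descriptive and secondary, the primary objectives are safety and tolerability, and no hypothesis is tested.

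**What to change.** In SAP 7.1 and Table 1:

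1. Make AUC0-2 the Part C exposure measure on Days 1, 28 and 84, and report AUC0-t on all three days.
2. Base Part C Rac on AUC0-2.
3. Keep AUC0-6, CLss/F and Vz/F as supportive. State that they are extrapolated with kel, and report how many patients have a calculable value and the percentage extrapolated.
4. Flag values with more than 20% of AUC0-6 extrapolated, but keep them in the summaries as SAP 15.2.2 does. Reporting only values at or below 20% would itself select patients by profile shape.
5. Remove AUC0-12 and AUC0-24 from Table 1 to match 7.1.

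Optionally, and only for profiles not yet collected, add a PK tube to the existing 6-hour serum draw as a supportive sample. AUC0-6 from those profiles would not be comparable with AUC0-6 from earlier ones, so AUC0-2 should remain the common measure.

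**Cost.** Items 1-5 are SAP wording. The optional sample costs one tube and its assay at a draw already scheduled. AUC0-2 captures less of the exposure, and it still needs extrapolation where the 2 h value is below quantification. It also does not separate accumulation from a dose increase between Day 1 and Day 28, so Rac still has to be read with the actual doses.
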